#### Frequentist linear mixed effects analysis:

In addition to this Bayesian approach, we will also utilize a frequentist approach to determine the response on UACR during each period. To estimate this response a linear mixed effects model with random intercepts and random slopes for treatment will be used. Fixed effects include treatment sequence, and treatment cycle. Baseline log-transformed UACR may be added as covariate. Appropriate contrasts will be implemented to assess the placebo subtracted response during the first and second cycle and to correlate the placebo adjusted UACR responses to dapagliflozin (fitted on the log-scale) during the two treatment periods. The variance-covariance pattern of the mixed effects model is assumed to be unstructured. If the model does not converge less stringent models will be considered.

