#### 10. STATISTICAL ANALYSIS

#### 10.1. Primary study parameter(s)

The change from baseline in UACR will be calculated using the values collected at day 5, 6 and 7 of each treatment and wash-out period. Because of the skewed distribution UACR will be log-transformed before analysis. The geometric mean of these 3 values (at baseline to end of treatment) will be calculated as log(UACRend/UACRbaseline) and the geometric mean change from baseline will be determined.

The study has two cycles for two treatment periods (dapagliflozin and placebo). For calculation of response, the difference in UACR change between dapagliflozin and placebo will be calculated during the first and second cycle. To this end a linear mixed effects model with random intercepts and random slopes for treatment will be used to determine the response during each period. Fixed effects include treatment sequence, and treatment cycle. Baseline log transformed UACR may be added as covariate. Appropriate contrasts will be implemented to assess the placebo substracted response during the first and second cycle and to correlate the placebo adjusted UACR responses to dapagliflozin (fitted on the log-scale) during the two treatment periods. The variance-covariance pattern of the mixed effects model is assumed to be unstructured. If the model does not converge less stringent models will be considered.

To determine if there is within individual variation in treatment response, we will fit a linear mixed model with correlated random intercepts and random slopes for treatment and include treatment period as a fixed effect. Subsequently, we will compare (using a maximum-likelihood ratio fit test) this model against a random intercept only model with treatment and treatment period as fixed effects.

In an additional supportive analysis, we will also dichotomize response. If the placebo adjusted difference in both cycles is greater than 20% in favor of dapagliflozin (using the linear mixed effects model), the patient will meet the response definition. We will then perform a McNemar test for the proportion of concordant response (response during the two cycles or no response during

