#### Heterogeneity treatment of effect analysis:

For those patients that completed both treatment cycles we will evaluate heterogeneity of treatment effects (HTE) across patients using a linear regression model with UACR response as the outcome. The model includes fixed effects for treatment and subject and a treatment-by-subject interaction, this allows each participant to have a different treatment effect. The statistical significance of patient-level HTE will be assessed by a likelihood test for the interaction term. In addition, we also fit a generalised linear mixed effect (LME) model with a random intercept and slope (for the treatment effect) to estimate the average treatment effect across all subjects. Fixed effects include treatment sequence, and treatment cycle in combination with an unstructured covariance structure.

Also we will use the linear mixed effects model as described above to determine if there is within individual variation in treatment response, we will fit a linear mixed model with correlated random intercepts and random slopes for treatment and include treatment period as a fixed effect. Subsequently, we will compare (using a maximum-likelihood ratio fit test) this model against a random intercept only model with treatment and treatment period as fixed effects.

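### Correlating cycle-1 and cycle-2 UACR responses fitted by a mixed model with one treatment slope per patient cannot test whether the response is reproducible

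*Combined protocol and SAP*

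**What the plan says.** SAP 5.1 (Frequentist linear mixed effects analysis) and protocol 10.1 describe the same model. The SAP states: "To estimate this response a linear mixed effects model with random intercepts and random slopes for treatment will be used". In the protocol, a "linear mixed effects model with random intercepts and random slopes for treatment will be used to determine the response during each period". On the fixed part, the SAP says "Fixed effects include treatment sequence, and treatment cycle", and it leaves one option open: "Baseline log-transformed UACR may be added as covariate". On covariance it says "The variance-covariance pattern of the mixed effects model is assumed to be unstructured", without stating whether this means the random effects or the residuals. Contrasts from the model are to give the placebo-subtracted response in each cycle and "to correlate the placebo adjusted UACR responses to dapagliflozin (fitted on the log-scale) during the two treatment periods".

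No random term in either document lets a patient's treatment effect differ between cycles.

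Protocol 4.4 and SAP 3.2 base the 20 patients on the hypothesis that responses to the first and second exposure correlate, with 0.6 as the value to detect. Protocol 10.1 also plans a supportive analysis that classes patients as responders at a 20% threshold in each cycle, using the mixed model, and compares concordant with discordant patients.

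**The concern.** Reproducibility on re-exposure is the stated hypothesis of the trial (protocol section 1) and the only basis for its size. A correlation can speak to it only if it is free to take low values when responses do not repeat. Here the model has already imposed one treatment effect per patient across both cycles, so correlating its fitted values returns the model's own assumption. A trial in which patients responded quite differently the second time would still report a correlation of 1. The responder concordance is inflated for the same reason if it is taken from the same fitted values.

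**Working it through.** **Inputs.** N = 20, alpha 0.05 (sidedness not stated), power above 80% and r = 0.6 come from protocol 4.4 and SAP 3.2. The model terms come from protocol 10.1 and SAP 5.1. The simulation settings in step 4 are assumptions.

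**1. The plan's own figure.** For a Fisher-z test of zero correlation, power = Φ(atanh(0.6)·√(20−3) − 1.96) = Φ(0.693 × 4.123 − 1.96) = Φ(0.898) = 81.5% two-sided. The N for 80% power is ((1.96 + 0.842)/0.693)² + 3 = 19.3, so 20. One-sided power is 88.7%, and a simulated two-sided t test of r gives 83.5%. The stated power reproduces, but it applies to a correlation that is free to vary.

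**2. The fitted contrast.** For patient i in cycle c on treatment T (1 = dapagliflozin, 0 = placebo), the fitted value is

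μ + sequence_i + cycle_c + βT + a_i + b_i·T.

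In dapagliflozin minus placebo, μ, the sequence effect, the cycle effect and the intercept a_i cancel:

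fitted response = β + b_i in cycle 1, and β + b_i in cycle 2.

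A fixed treatment-by-cycle term adds a constant δ to cycle 2, the same for every patient. The two columns being correlated are then b_i plus a constant, twice. Their correlation is 1 if the fitted slopes vary between patients. If the slope variance is estimated as zero, it is undefined.

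**3. The optional baseline covariate.** One baseline value per patient cancels as above. A period-specific baseline x with coefficient γ, kept at its observed values, gives β + b_i + γ(x_D − x_P), where the bracket differs by cycle. The only cycle-varying part is then baseline variation. If the bracket is independent of b_i and between cycles, the correlation is var(b)/(var(b) + γ²·var(x_D − x_P)), which contains no cycle-specific response.

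**4. Simulation.** Settings were 20 patients per trial and 40 trials at each of five true between-cycle correlations. The four orders had one dapagliflozin and one placebo period per cycle. On the log scale the mean effect was −0.4, the response SD 0.4, and the SDs of the other within-trial components 0.2 to 0.3. The model had fixed sequence, cycle and treatment, with a random intercept and treatment slope.

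| True correlation | Observed differences: mean r (range) | Fitted, no baseline covariate | Fitted, period-specific baseline: mean r (range) |
|---|---|---|---|
| −0.6 | −0.60 (−0.88 to −0.37) | 1.000000 in all 40 | 0.57 (−0.32 to 1.00) |
| 0 | −0.04 (−0.59 to 0.45) | 1.000000 in all 40 | 0.89 (0.14 to 1.00) |
| 0.3 | 0.33 (−0.09 to 0.72) | 1.000000 in all 40 | 0.93 (0.25 to 1.00) |
| 0.6 | 0.60 (0.20 to 0.86) | 1.000000 in all 40 | 0.94 (−0.69 to 1.00) |
| 0.9 | 0.90 (0.78 to 0.97) | 1.000000 in all 40 | 0.99 (0.81 to 1.00) |

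Adding a fixed treatment-by-cycle term left the third column at 1.000000. The last column is below 1 but does not estimate the true value: it averages 0.89 when the truth is 0, and 0.57 when the truth is −0.6.

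**5. Responder concordance.** By step 2, without a treatment-by-cycle term or a period-varying covariate, a patient's two fitted responses are identical, so nobody with complete data can be discordant. With the interaction term, only patients whose slope lies within the shift δ of the threshold can be. I give no percentage, because it would depend on the assumed effect and error SD.

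**The case against.** **Observed differences are already planned.** Protocol 10.1 and SAP 5.1 both say that the difference between dapagliflozin and placebo is calculated in each cycle. However, the protocol goes straight on to name the mixed model as the means of doing this, and the SAP says that the correlated responses are fitted ones. If observed differences are meant, the text needs to say so.

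**The covariance wording may mean more.** An unstructured residual matrix over the four treatment-by-cycle cells would allow a between-cycle correlation to be estimated. The random intercept and slope would then be redundant, and neither document describes such a model. What stands is that the wording is ambiguous.

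**The correlation need not be exactly 1.** A reader might infer that it is 1 whatever the data. The documents do not support that: the baseline covariate is optional and could vary by period, and the fallback to simpler models could remove the slope. This part of the objection stands. It does not rescue the statistic, which in those cases is either undefined or moved by baseline differences.

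**Treatment is missing from the fixed effects.** A reader might infer that the average effect has no parameter, since the heterogeneity section pairs that aim with a list lacking treatment: "to estimate the average treatment effect across all subjects. Fixed effects include treatment sequence, and treatment cycle". A list introduced by a word such as include need not be complete. The same section names treatment as fixed in the interaction regression and in the random-intercept comparator. This is a wording gap, not evidence of a wrong model, and the simulation above, which included fixed treatment, does not bear on it.

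**Other analyses address individual response.** This stands. The SAP puts the Bayesian analyses first and also plans the interaction and likelihood-ratio tests. None of them uses the fitted correlation, but none reports a cycle-to-cycle correlation either.

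**Conclusion.** The concern holds for the fitted cycle-to-cycle correlation. Under the model as described it equals 1 when the estimated slope variance is above zero and no period-varying baseline is used. Otherwise it is undefined, or it departs from 1 for reasons unrelated to repeat response. It cannot test the hypothesis on which the 20 patients rest. The protocol's supportive concordance analysis, which does not appear in SAP section 5, is inflated if it uses the same fitted values.

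The algebra needs only the single slope per patient. The simulation SDs and treatment orders are assumptions, and the value 1 does not depend on them. It would be wrong to infer that the trial as a whole yields no evidence on individual response: the Bayesian analyses, the treatment-by-subject interaction test and the likelihood-ratio test of random slopes are not affected.

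**What to change.** In protocol 10.1 and SAP 5.1, state one of the following:

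- The cycle-to-cycle correlation, and any concordance, is computed from each patient's observed dapagliflozin-minus-placebo difference in log UACR change within each cycle, with a Fisher-z 95% CI. The 81.5% power in step 1 then applies to the reported quantity.
- Reproducibility is reported, with a CI, as slope variance / (slope variance + error variance of a per-cycle difference). The model has fixed treatment and period, and random patient and patient-by-treatment terms. The slope is the patient's deviation in the dapagliflozin-minus-placebo effect. With independent period residuals of variance σ², the error variance of a per-cycle difference is 2σ².

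Add that fitted or BLUP responses are not correlated between cycles. Say that each cycle holds one dapagliflozin and one placebo period, because the first option needs this and the design sections say only that the order is random. As a minor clarification, list treatment among the fixed effects.

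The cost is wording in two documents. The visits, samples and sample size stay as they are.

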### 8.5. Replacement of individual subjects after withdrawal

Patients that meet the inclusion criteria will be invited for participation in the study. When a patient agrees to participate in the study, patients will be invited for screening and informed consent is signed. After the screening visit, eligible patients will proceed to the second visit. When patients decide to withdraw after start of the treatment period, they will be replaced so that twenty patients will complete the full study protocol.

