#### 3.1. General Design and Plan

Subjects with UACR >20 mg/g (2.26 mg/mmol) with a diagnosis of type 2 diabetes who meet the inclusion criteria will be invited for screening. After the screening visit, eligible patients will proceed to the randomization visit. Patients will be randomly assigned to a cross-over study consisting of two periods of 1-week treatment with dapagliflozin and two periods of 1-week treatment with placebo in random order with a 1-week wash-out period between every treatment period to avoid cross-over effects. Based on a prior study, effects of dapagliflozin on UACR, blood pressure, body weight, fasting plasma glucose and eGFR were fully present after 4 days. We will therefore ask patients to collect urine after 3, 5, 6, and 7 days. Due to day-to-day variation in UACR we are collecting multiple urine samples to increase precision and therefore collect urine at 3, 5, 6, and 7 days. We will also collect urine after 1 day to further delineate the time-course of the response to dapagliflozin and assess if the treatment effect on UACR is directly present after 1 day. Blood pressure and body weight will be recorded, and blood samples will be taken at the time points described below and in the table. Overall, a 1-week treatment period is considered sufficient to detect effects on primary and secondary outcomes.

Since data collection will be performed at home using wearable devices and digital technologies, instructions will be provided during the randomization visit to perform data collection and study procedures at home. Data collection and measurements will be performed in each treatment period as indicated in Figure 1. Bottles with smart caps that

Statistical Analysis Plan Page 4 of 13

allow real-time monitoring of adherence, blood pressure monitors, body analysis scales and study medication will be provided at the randomization visit. Patients receive four numbered bottles with seven tablets in each bottle, according to their randomized treatment schema. Patients will be instructed to take the study medication once daily, in the morning.

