#### 3.2. Sample Size

The sample size for this study is based on the hypothesis that the response to dapagliflozin is reproducible upon re-exposure and thus correlates between the first and second exposure while no correlation will be detected during placebo patients. A prior retrospective study found that during intervention in the renin-angiotensin-system responses in proteinuria correlate with correlation coefficients ranging between 0.7 to 0.9. Since this was a retrospective study, we assume a more conservative correlation coefficient of 0.6. A sample size of 20 patients provides >80% power (alpha 0.05) to detect a correlation coefficient of 0.6.

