#### 5.1. Analysis of primary and secondary study outcome

The change from baseline in UACR will be calculated using the values collected at day 5, 6 and 7 of each treatment and wash-out period. Because of the skewed distribution UACR will be log-transformed before analysis. The geometric mean of these 3 values (at baseline to end of treatment) will be calculated as log(UACRend/UACRbaseline) and the geometric mean change from baseline will be determined.

The study has two cycles of two treatment periods (dapagliflozin and placebo). For the calculation of response, the difference in log-transformed UACR change between dapagliflozin and placebo will be calculated during the first and second cycle. Patient level Bayesian analysis:

First, a Bayesian analysis will be conducted to calculate the posterior probability of dapagliflozin producing a clinically meaningful response on UACR within each individual patient relative to placebo for both treatment cycles combined. Thus for every patient, data of each cycle is combined and expressed in the form of a likelihood function with non-informative priors to calculate the posterior distribution. A clinically meaningful response on UACR is defined as the placebo subtracted percentage UACR change during the first and second cycle with different thresholds of 10%, 20% or 30% reduction in UACR. Population level Bayesian hierarchical analysis:

Subsequently, individual patient results on UACR will be combined to conduct a Bayesian hierarchical analysis to calculate the posterior probabilities of a clinically meaningful response at the population level (10%, 20%, and 30%). Therefore, responses on UACR from each patient will be aggregated into a sample mean and variance, assuming a normal distribution centred around the patient's true mean effect and variance. The Bayesian hierarchical model is defined as:

$$Y_{ij} \sim N(\alpha_i + \beta_i X_{ij}, \sigma_i).$$

Were  $Y_{ij}$  is the placebo subtracted UACR response for the  $i^{th}$  subject at time j and is described by  $x_{ij}$  ( $x_{ij}=1$  if treated with dapagliflozin; =0 if placebo treated). The subject specific intercept and slope were modelled as  $a_i \sim N(a_0, \tau_a^2)$  and  $\beta_i \sim N(\beta_0, \tau_\beta^2)$  respectively. Again, we used non-informative prior for  $a_0$ ,  $\beta_0$ ,  $\tau_a^2$ ,  $\tau_\beta^2$ ,  $\sigma_i$ .

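### The UACR response is adjusted for time inconsistently, and sequence and cycle terms cannot remove a first-versus-second-period effect from the cycle responses

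*Combined protocol and SAP*

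**What the plan says.** SAP 5.1 sets up two cycles, each made of two treatment periods, and defines response within a cycle: "the difference in log-transformed UACR change between dapagliflozin and placebo will be calculated during the first and second cycle". Protocol 10.1 uses the same definition. Time then enters the UACR models as follows.

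- **No time term.** The Bayesian hierarchical model in SAP 5.1 has only a patient intercept and a patient treatment slope ("The subject specific intercept and slope were modelled as" normal distributions). The subject-by-treatment regression under the heterogeneity heading has treatment, subject and their interaction.
- **Sequence and cycle.** The frequentist mixed model, whose contrasts give the cycle responses and their correlation, states "Fixed effects include treatment sequence, and treatment cycle" (SAP 5.1 and protocol 10.1). The mixed model for the average effect, under the heterogeneity heading, uses the same terms.
- **Treatment period.** The likelihood ratio comparison of random-slope and random-intercept models is to "include treatment period as a fixed effect" (SAP 5.1 and protocol 10.1).

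No reason is given for the differences. The order of treatments is described only as "two periods of 1-week treatment with placebo in random order with a 1-week wash-out period between every treatment period". No list of permitted sequences appears.

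**The concern.** The trial exists to separate true individual response from temporal and random variation, and its sample size rests on the correlation between the two cycle responses. The model that feeds that correlation should therefore remove time effects that could pass for individual response. Its two listed terms cannot do so for the contrast of interest. What is left depends on treatment order and not on the patient's pharmacology. It can move patients across the 20% and 30% limits, weaken a true correlation between cycles, and make the heterogeneity test reject too often.

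**Working it through.** **Inputs.** From the documents: N = 20, alpha 0.05 (two-sided assumed), planning correlation 0.6, two cycles of two periods, and response thresholds of 10%, 20% and 30%. Assumed, because the documents give no values: a period shift d of 0.1 to 0.2 log units, and a noise SD of 0.4 for one cycle response. D is dapagliflozin and P is placebo.

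**1. The plan's own figure.** The SAP states: "A sample size of 20 patients provides >80% power (alpha 0.05) to detect a correlation coefficient of 0.6". By Fisher z, power = Φ(atanh(0.6)·√17 − 1.96) = Φ(2.858 − 1.96) = 81.5%. A simulated t-test of r gives 83.6%. The stated figure reproduces.

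**2. Why the listed terms cancel.** Write a patient's UACR change in a period as intercept + sequence + cycle + period effect + treatment effect. Within one cycle, D minus P removes the intercept, the sequence effect and the cycle effect, since both periods share them. The period effects do not cancel. If change in the first period of a cycle is higher by d, the cycle response is shifted by +d when D comes first and by −d when P comes first.

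**3. Size in one cycle response.** For a true 20% reduction, the observed reduction is 1 − 0.8·exp(±d):

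- d = 0.1: 11.6% or 27.6%
- d = 0.2: 2.3% or 34.5%

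**4. The response pooled over two cycles.** Noise-free fits, true reduction 20% in everyone:

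| Order | First period of each cycle +10% | Period 1 only +10% |
|---|---|---|
| DPDP | 12.0% | 16.1% |
| DPPD | 20.0% | 16.1% |
| PDDP | 20.0% | 23.7% |
| PDPD | 27.3% | 23.7% |

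The results are identical with no time term and with sequence plus cycle. With a four-level period term, every entry returns to 20.0%. So an equal shift cancels for DPPD and PDDP only; an unequal one reaches all four orders.

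**5. Correlation between cycles.** Let σ² be the variance of a cycle response.

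- Four balanced orders: the shift adds d² to the variance and nothing to the covariance, so r becomes r·σ²/(σ² + d²).
- Only DPDP and PDPD: the shift adds d² to both, so r becomes (r·σ² + d²)/(σ² + d²).

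With noise variance 0.16 and r = 0.6, σ² = 0.16/0.4 = 0.40. At d = 0.2, r falls to 0.6/1.10 = 0.545. With a true slope SD of 0.35, σ² = 0.1225 + 0.16 = 0.2825 and r = 0.43. At d = 0.2 this falls to 0.38. Simulated power with four orders (where two figures appear, they are the range over separate simulations):

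| d | r = 0.6, unadjusted | r = 0.6, period-adjusted | r = 0.43, unadjusted | r = 0.43, period-adjusted |
|---|---|---|---|---|
| 0 | 84% | 78% | 49–50% | 44–45% |
| 0.1 | 81% | 78% | 46–47% | 45% |
| 0.2 | 73% | 78% | 37–39% | 45–46% |

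Under no true patient differences and d = 0.2, the four orders give a significant positive correlation in 2.4% of trials, which is the nominal rate. If only DPDP and PDPD were used, the expected r is 0.04/(0.16 + 0.04) = 0.20, and 13–14% of trials are significant, against about 2.5–3% with period adjustment.

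**6. Subject-by-treatment test.** Rejection rate with no true heterogeneity, by shift in units of the residual SD of one period:

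| Shift | Four orders, no period term | DPDP/PDPD only, no period term |
|---|---|---|
| 0.5 | 7% | 15% |
| 1.0 | 12.5% | 59% |

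A period term brings these to about 5%. A noise SD of 0.4 per cycle response corresponds to 0.4/√2 = 0.28 per period, so d = 0.2 is about 0.7 residual SD.

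**The case against.** **No period effect is documented, and the outcome already removes slow drift.** This stands. Response is change from the preceding run-in or wash-out, so a gradual trend in UACR level largely drops out. Only a systematic difference in one-week change, shared by patients, matters. A d of 0.2 is large: the 36.2% reduction in protocol 6.3 is −ln(0.638) = 0.45 log units, so 0.2 is a little under half of it. The bias is potential, not shown.

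**Adjustment is not free.** This stands too. At d = 0.1 it brings no gain in power. At r = 0.6 with d = 0 it costs about 6 points and takes power below the stated 80%.

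**The lists of fixed effects may be shorthand.** Treatment is not listed for the frequentist mixed model either, although its cycle contrasts require it. That makes the wording incomplete, but a reader cannot supply a period term from it.

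**Stronger readings that a reader might infer, and that the documents do not support:**

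- *Every patient's overall response is biased.* That holds for cycle-specific responses. In the pooled two-cycle response used in the patient-level Bayesian analysis, an equal shift cancels for DPPD and PDDP.
- *The plan will produce a false correlation between cycles.* That needs orders that repeat (DPDP and PDPD only). The documents say random order and state no such restriction.
- *One model certainly adjusts for four periods.* The SAP does not state the number of levels. Its frequentist paragraph speaks of two treatment periods where it appears to mean cycles, so the term may be a cycle effect. In that case no model adjusts for period.

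**Conclusion.** The concern holds in this form. The time terms differ between models for the same UACR response without a stated reason, and sequence and cycle main effects remove none of a first-versus-second-period effect from the within-cycle contrast. Such an effect stays in every cycle-specific response, and in the pooled response unless order and shift happen to balance.

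The size depends on an assumed d. At 0.1 log units, order alone moves a true 20% reduction to 12% or 28%. At 0.2, with four balanced orders and a noise SD of 0.4, power of the correlation test falls from about 84% to 73% at r = 0.6 and from about 49% to 39% at r = 0.43. The subject-by-treatment test can also reject too often. With four balanced orders the main harm to the correlation is dilution, not a false positive. If the period effect is small, the practical gain from adjustment is consistency and protection of individual classifications, not power.

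**What to change.** - In protocol 10.1 and the frequentist response model of SAP 5.1, replace treatment cycle by treatment period as the fixed time effect, and state that it has four levels. Say the same for the random-slope comparison.
- Add the same term to the Bayesian hierarchical model and to the subject-by-treatment regression.
- Derive the cycle responses, their correlation and the responder classification from period-adjusted values.
- State the permitted sequences. Random order as written does not exclude DDPP or PPDD, for which a within-cycle response does not exist.
- The patient-level Bayesian analysis can stay unadjusted. One patient has four periods, while an intercept, a treatment effect and three period contrasts make five parameters. Say in the SAP that it carries no period adjustment.

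Cost: wording only, with no new data. The mixed model gains two parameters (three period contrasts in place of one for cycle); models that now have no time term gain three. If there is no period effect, the correlation test loses up to about 6 points of power (about 84% to 78% at r = 0.6 with four orders), and the sample size statement should acknowledge this.
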